## **2. STUDY OBJECTIVES AND ENDPOINTS**

### **2.1. Objectives**

#### **2.1.1. Primary Objective**

- To estimate the proportion of subjects who flare within 40 weeks following withdrawal of ETN in subjects who have achieved ASDAS CRP less than 1.3 (inactive disease).

#### **2.1.2. Secondary Objectives**

- To estimate time to flare after withdrawal of ETN, and to compare it to that in subjects from B1801031 who continued ETN therapy.
- To estimate the efficacy of 12 weeks of retreatment in subjects who experience a flare after withdrawal of ETN.
- To estimate the efficacy of ETN over 24 weeks of initial treatment.
- To estimate the safety and tolerability of ETN in this population.

### **2.2. Endpoints**

This study will not use an Endpoint Adjudication Committee.

#### **2.2.1. Primary Endpoint**

- The primary endpoint is the occurrence of flare (defined as an ASDAS ESR greater than or equal to 2.1) within 40 weeks following withdrawal of ETN.

#### **2.2.2. Secondary Endpoints and Outcome Measures**

The following key secondary endpoint will be estimated:

- The time to flare following withdrawal of ETN (as measured from treatment withdrawal until ASDAS ESR greater than or equal to 2.1).

The following secondary endpoints and outcome measures will be estimated within 40 weeks following withdrawal of ETN and during the 12 week re-treatment period (if applicable):

- Occurrence of ASDAS CRP less than 1.3 (inactive disease);
- Occurrence of ASAS 20 and ASAS 40;
- Occurrence of ASAS partial remission;
- ASDAS;
- Occurrence of ASDAS major improvement and clinically important improvement;

- Nocturnal and total back pain;
- Bath Ankylosing Spondylitis Functional Index (BASFI) and its components;
- Bath Ankylosing Spondylitis Disease Activity Index (BASDAI) and its components;
- Occurrence of BASDAI 50;
- High sensitivity C Reactive Protein (hsCRP);
- Health Outcomes Assessments using the following instruments: EuroQoL-5D Health Questionnaire (EQ-5D), SF-36 and Work Productivity and Activity Impairment (WPAI);
- MRI SIJ/spine as measured by Spondyloarthritis Research Consortium of Canada (SPARCC).

The following secondary endpoint will be estimated over 12 weeks following re-treatment of subjects who flare:

- Time to ASDAS inactive disease after re-treatment.

Other endpoints:

- Subject Assessment of Disease Activity (SADA);
- Physician Global Assessment (PGA);
- Bath Ankylosing Spondylitis Patient Global Assessment Score (BAS-G);
- Tender and swollen joint counts (44 count);
- Dactylitis and enthesitis score (Maastricht Ankylosing Spondylitis Enthesitis Score [MASES]).

### **2.2.3. Safety Endpoints**

Safety will be assessed throughout the study. The following variables will be assessed: physical examination, vital signs, hematology, chemistry, urinalysis, premature withdrawal, inflammatory bowel disease (IBD), psoriasis, and uveitis evaluations, adverse events and serious adverse events during the study.

### 3. STUDY DESIGN

This multicenter, open-label, three period study will evaluate withdrawal and retreatment of ETN in subjects with nr-ax SpA who achieved an adequate response, as measured by ASDAS CRP less than 1.3 (inactive disease) following 24 weeks of treatment. The study is expected to randomize approximately 200 subjects in Period 1, in order to have approximately 96 subjects qualify for Period 2.

#### 3.1. Period 1

This is an open-label, 24-week period in which all eligible subjects with nr-ax SpA will be enrolled and treated with ETN 50 mg once weekly plus a stable background NSAID at the optimal tolerated anti-inflammatory dosage as determined by the investigator. The target for this period is therapeutic response defined as achieving Ankylosing Spondylitis Disease Activity Scale C-reactive protein (ASDAS CRP) less than 1.3 at Week 24. Subjects who qualify at Week 24 will enter Period 2 after all Period 1 procedures are completed. Subjects who do not achieve ASDAS CRP less than 1.3 will not enter Period 2 and will complete the study following the Week 28 day follow-up phone call/visit.

#### 3.2. Period 2

The Week 24 visit ends Period 1 and marks the beginning of Period 2. This is a 40-week withdrawal period where subjects will discontinue ETN following the Week 24 dose, yet maintain the background NSAID. If the subject has not flared by the Week 64 visit, their participation in the study is complete.

#### 3.3. Period 3

Subjects who flare (defined as an ASDAS ESR greater than or equal to 2.1) during Period 2 will enter a retreatment period and receive approximately 12 weekly doses of open-label ETN. Subjects experiencing increased disease activity can come into the office any time for an evaluation; if flare criteria are met, open-label ETN is started at this unscheduled visit. If the subject has experienced increased disease activity during Period 2, but does not meet the protocol defined criteria for flare, it is the investigator's judgment to determine if the subject should remain in the study or discontinue the study to pursue alternative treatment.

#### 3.4. Follow-up

[figure not shown]
A safety follow-up phone call/visit will only be completed for subjects who:

- Receive investigational product (IP) in Period 1, but who do not enter Period 2, or,
- Enter Period 2 and discontinue from the study *before* the Week 28 visit or,
- Enter Period 3 (Retreatment period).

The purpose of this visit is to assess any new and/or ongoing adverse events and will be performed approximately 28 days after the last dose of IP. This follow-up visit will be done by telephone, unless local regulations require a visit to the study site.

A safety follow-up visit does not need to be completed for subjects who discontinue from the study after the Week 28 visit and who do not enter Period 3 for retreatment.

**Figure 1. Study Schematic**

†Flare is defined as ASDAS ESR  $\geq 2.1$

\*The follow-up visit is only required 28 days following the last dose of IP. This will occur either at the end of Period 1 (for subjects that don't qualify for Period 2) or at the end of Period 3 (for subjects who flare and require retreatment).

\*\*Subjects who flare at Week 64 will receive 12 weeks of OL ETN and will have their final study visit at Week 76 and their follow-up visit 28 days later.

#### 4. SUBJECT SELECTION

This study can fulfill its objectives only if appropriate subjects are enrolled. The following eligibility criteria are designed to select subjects for whom participation in the study is considered appropriate. All relevant medical and nonmedical conditions should be taken into consideration when deciding whether a particular subject is suitable for this protocol.

##### 4.1. Inclusion Criteria – Period 1

Subject eligibility should be reviewed and documented by an appropriate member of the investigator's study team before subjects are included in the study. An eligibility worksheet will be provided to document the review of the inclusion and exclusion criteria.

Subjects must meet all of the following inclusion criteria to be eligible for enrollment into the study:

1. Evidence of a personally signed and dated informed consent document indicating that the subject has been informed of all pertinent aspects of the study.
2. Subjects who are willing and able to comply with scheduled visits, treatment plan, laboratory tests, and other study procedures.
3. Male subjects able to father children and female subjects of childbearing potential and at risk for pregnancy must agree to use a highly effective method of contraception throughout the entire study and for 28 days after the last study visit.
  - Have undergone a documented hysterectomy and/or bilateral oophorectomy;
  - Have medically confirmed ovarian failure; or

Achieved postmenopausal status, defined as follows: cessation of regular menses for at least 12 consecutive months with no alternative pathological or physiological cause; and have a serum follicle-stimulating hormone (FSH) level confirming the post-menopausal state

4. Duration of symptoms of  $\geq 3$  months and  $< 5$  years at the time of consent.
5. Diagnosis of ax SpA as defined by the ASAS criteria (Appendix 2).

The ASAS criteria state that subjects have to have  $\geq 3$  months of back pain and age of onset  $< 45$  years, and:

- Sacroiliitis on imaging plus 1 SpA feature

OR

- Positive Human Leucocyte Antigen B27 (HLA-B27) plus 2 SpA features.

Sacroiliitis on imaging is defined as either:

- Active inflammation on MRI highly suggestive of sacroiliitis associated with SpA

OR

- Defined radiographic sacroiliitis according to the Modified NY criteria\*\*

\*\*Subjects in this study cannot meet the criteria based on the second bullet (since defined radiographic sacroiliitis is an exclusion criterion). In order to meet the imaging criteria for ASAS, subjects must have positive sacroiliitis on MRI based on readings performed by the central imaging vendor. This criterion **cannot** be based on local MRI evaluation or historical MRIs.

If a subject has negative sacroiliitis on MRI, then they must have positive HLA-B27 plus 2 SpA features. Conversely, if a subject is HLA-B27 negative, then they must have positive sacroiliitis on MRI and at least 1 SpA feature. (See flowchart in [Appendix 6](#)).

The SpA features are listed below and defined in [Appendix 4](#).

- Inflammatory back pain;
  - Arthritis;
  - Enthesitis (heel);
  - Uveitis;
  - Dactylitis;
  - Psoriasis;
  - Crohn's/ Colitis;
  - Good response to NSAIDs;
  - Family history of SpA;
  - HLA-B27;
  - Elevated hsCRP.
6. Subjects must have positive MRI findings (active inflammation on MRI highly suggestive of sacroiliitis associated with SpA) and/or positive hsCRP (defined as hsCRP >3 mg/l).
  7. Active symptoms defined by an ASDAS CRP greater than or equal to 2.1 at the screening visit.
  8. Back pain with a less than favorable response to current intake of an NSAID at the optimal tolerated dose as determined by the investigator. Subjects must have experienced less than favorable response to at least 2 NSAIDs (including the current one) taken separately at the optimal tolerated dose with a total combined duration of >4 weeks.
  9. Subject must be taking a stable dose of an NSAID for at least 14 days before the first dose.
  10. Female or male 18 years or older (20 or older if required by local regulations) but less than 50 at the time of consent.

11. In the opinion of the investigator, subject is reasonable candidate for treatment with ETN.
12. No contraindication to MRI examination (metal implants or inability to lie flat for 30-60 minutes for example).
13. Negative serum pregnancy test performed at screening, negative urine pregnancy test performed prior to the first dose and negative serum pregnancy test collected for analysis prior to the first dose.
14. Ability to self-inject investigational product or have a designee who can do so.
15. Ability to store injectable investigational product under refrigerated conditions.
16. Demonstrated an adequate screening for tuberculosis (TB) in accordance with local country guidelines.
17. Subject is able to complete health outcomes assessments and investigational product diary.
18. In Germany only: Subjects who are not eligible to get new spine and/or pelvic x-rays, due to local regulations must have had these x-rays taken within 12 months prior to the screening visit. The central reader must consider the x-rays to be acceptable for evaluation of sacroiliitis.

#### **4.2. Inclusion Criteria – Period 2**

1. Completion of Period 1.
2. Subjects must achieve ASDAS CRP (inactive disease) less than 1.3 at the Week 24 visit in order to be eligible to enter Period 2.

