Abbreviations: BL=baseline; IBD = inflammatory bowel disease, IP = investigational product; TB=tuberculosis; → = ongoing/continuous event; HLA-B27 = human leucocyte antigen B27; hsCRP = high sensitivity c-reactive protein; SIJ = sacroiliac joint; MRI = magnetic resonance imaging; BASDAI = Bath Ankylosing Spondylitis Disease Activity Score; BASFI = Bath Ankylosing Spondylitis Functional Index; BAS-G = Bath Ankylosing Spondylitis Patient Global Assessment Score; EQ-5D = EuroQol EG-5D Health State Profile; SF-36 = 36-Item Short-Form Health Survey; WPAI = Work Productivity and Activity Impairment Questionnaire .

- a. Day relative to start of study treatment (Day 1).
- b. Screening visit should occur within 4 weeks (28 days) of BL visit but no less than 5 days before BL visit. The screening period may be extended up to 42 days if repeat imaging is required or when tuberculosis prophylactic therapy is started during the screening period.
- c. ASDAS CRP will be calculated at the Week 24 visit, which will determine if subjects are eligible to enter Period 2. If the ASDAS CRP is <1.3 at Week 24, subjects will return to the site at Week 28 to continue with the Period 2 procedures. If the Week 24 ASDAS CRP is ≥1.3, the subject should be notified by phone that their participation in the study is complete. A follow-up call will be conducted in place of the Week 28 visit to assess new and ongoing adverse events and medication taken to treat them since the last dose of investigational product.
- d. Follow-up: For subjects who discontinue the study during Period 1, or enter Period 2 and discontinue from the study *before* the Week 28 visit, or subjects who enter Period 3, there will be a follow-up telephone call to assess new and ongoing adverse events and the medications taken to treat them. This call will be approximately 28 days after the last dose of IP. No follow-up is needed if subjects enter Period 2 and do not experience a flare. If required by local regulations, the follow-up visit may be conducted at the study site.

- e. The first visit of the Retreatment period (Period 3) may occur at the same time as a regularly scheduled visit during Period 2 or it may occur as an unscheduled visit.

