#### **9.2. Efficacy Analysis**

##### **9.2.1. Analysis of the Primary Endpoint**

The primary endpoint, the occurrence of flare (ASDAS ESR greater than or equal to 2.1) in Period 2 will be summarized descriptively as the percent with flare with 95% confidence interval. This estimate will include all subjects who qualify for the retreatment interval and have at least one evaluation after treatment is withdrawn.

ASDAS is calculated from the following parameters:

1. Total back pain (BASDAI question 2);
2. Subject global assessment of disease activity;
3. Peripheral pain/swelling (BASDAI question 3);
4. Duration of morning stiffness (BASDAI question 6);
5. C-reactive protein (CRP) in mg/litre or ESR in mm/h.

The ASDAS score is then calculated as follows:

ASDAS CRP = (0.121 x total back pain) + (0.110 x subject global) + (0.073 x peripheral pain/swelling) + (0.058 x duration of morning stiffness) + (0.579 x Ln(CRP+1)).

ASDAS ESR = (0.08 x total back pain) + (0.11 x subject global) + (0.09 x peripheral pain/swelling) + (0.07 x duration of morning stiffness) + (0.29 x  $\sqrt{\text{ESR}}$ ).

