6. ANALYSES AND SUMMARIES

6.1. Primary Endpoint(s)

6.1.1. ASDAS flare

6.1.1.1. Primary Analysis

Endpoint: ASDAS flare (ASDAS ESR greater than or equal to 2.1).

- Analysis time points: Period 2 (over entire period).
- Analysis population: Period 2 FAS.
- method of imputation for missing data: LOCF.
- Primary analysis methodology: Descriptive summary only of proportion flared at each period 2 visit.

Reporting results:

- Descriptive: proportions (n/N) and 95% Confidence interval) at each period 2 visit.

- Supporting objective and Decision rule: Primary Objective.

Additional analyses for primary endpoint

- Method of imputation for missing data: None .
- Analysis methodology: Kaplan Meier estimate of time to flare and Cox proportional hazards model for evaluation of covariates and estimation of hazard compared to prior study B1801031 which had no withdrawal of treatment.
- Supporting objective and Decision rule: Primary Objective.
- Covariates used (Cox model): Covariates for the Cox regression model of time to flare will include, in addition to study (B1801031 vs B1801381), age, sex, geographic region, baseline CRP (normal vs. high), baseline MRI status (negative vs. Positive), disease duration, prior NSAID response (good vs. not) plus ASDAS values at weeks 12 and 24 or, in a separate model, sustained ASDAS inactive disease in period 1, defined as ASDAS ESR<1.3 at Week 12 or Week 16 (where ASDAS may not be greater than 2.1 at either time point) and at Week 24. Binary variables with small frequencies in either study will not be included in the Cox regression model.

Reporting results:

- Estimation:

Kaplan-Meier estimates of 25%, median and 75% survival and 95% confidence intervals.
Cox model based hazard ratio estimates for covariates and study.
- Tables: Present table with just HR and CI for “study” for 4 models:
 1. study only
 2. study plus baseline variables
 3. study plus baseline variables plus ASDAS continuous at 2 times
 4. study plus baseline variables plus sustained ASDAS remission
- Figures:

Kaplan Meir plots showing both studies flare events.

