Appendix 2. STATISTICAL METHODOLOGY DETAILS

Appendix 2.1. Flare using ASDAS CRP

Subjects will be entered into the retreatment period based on occurrence of flare, defined as an ASDAS ESR value ≥ 2.1 during the withdrawal period. A secondary set of efficacy endpoint analyses for the retreatment period will include only those subjects who also had an ASDAS CRP value ≥ 2.1 .

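### Period 2 entry is judged on ASDAS CRP and flare on an absolute ASDAS ESR cut, so a subject can enter already at the flare threshold, and no planned analysis of the primary proportion isolates such subjects

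*Protocol*

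**What the plan says.** **Entry.** Protocol 4.2 gives two conditions for Period 2: completing Period 1, and "Subjects must achieve ASDAS CRP (inactive disease) less than 1.3 at the Week 24 visit in order to be eligible to enter Period 2". A footnote to the Schedule of Activities confirms which score decides: "ASDAS CRP will be calculated at the Week 24 visit, which will determine if subjects are eligible to enter Period 2". Neither place sets a condition on ASDAS ESR.

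**Event.** Protocol 2.2.1 reads: "The primary endpoint is the occurrence of flare (defined as an ASDAS ESR greater than or equal to 2.1) within 40 weeks following withdrawal of" etanercept. SAP 6.1.1.1 repeats it: "Endpoint: ASDAS flare (ASDAS ESR greater than or equal to 2.1". The cut is absolute. No rise from the Week 24 value is required.

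**Where the SAP allows for disagreement between the scores.** Appendix 2.1 notes that retreatment is triggered by ASDAS ESR and adds: "A secondary set of efficacy endpoint analyses for the retreatment period will include only those subjects who also had an ASDAS CRP value" of at least 2.1. This covers the retreatment period only.

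**Other planned uses of Week 24 scores.** SAP 6.1.1.1, 6.4 and Appendix 2.2 analyse flare by sustained inactive disease, defined as ASDAS ESR below 1.3 at Week 24 and also at Week 12 or 16, with neither of those two values above 2.1. One Cox model adjusts for ASDAS at Weeks 12 and 24, without naming the version. SAP 3.4 and 6.2.2 summarise ASDAS ESR by visit, raw and as change from the last value before withdrawal.

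**The concern.** The primary objective is the proportion who flare after withdrawal among subjects with inactive disease. If inactive is judged by one score and flare by another, a subject can be on both sides at time zero. Such a subject counts as a flare at the first Period 2 visit, four weeks after the Week 24 visit, although nothing has changed since withdrawal. That would raise the flare proportion and shorten the key secondary endpoint, time to flare. The single-arm proportion is the most exposed result, because it has no comparator in which the same artefact could appear.

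**Working it through.** **Inputs.**
- Score weights: Protocol 9.2.1 and SAP 3.1.
- Item units (0 to 10 cm) and the CRP floor (hsCRP below 2 mg/L is set to 2): SAP 3.1. The protocol formula has no floor.
- 70% expected to flare, about 96 entering Period 2, half-width about 10%: Protocol 9.1.

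**The plan's own precision.** 1.96 × √(0.70 × 0.30 / 96) = 0.092, or 9.2 points (exact interval: 9.6). This agrees with the stated figure of about 10%.

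**Can both conditions hold on one day?** With all four items equal to x cm, the item weights add to 0.121 + 0.110 + 0.073 + 0.058 = 0.362 (CRP version) and 0.08 + 0.11 + 0.09 + 0.07 = 0.35 (ESR version). So:
- ASDAS CRP = 0.362x + 0.579 × ln(CRP + 1)
- ASDAS ESR = 0.35x + 0.29 × √ESR

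For x = 1.8, CRP 2, ESR 26:
- ASDAS CRP = 0.652 + 0.636 = 1.29, below 1.3, so the subject enters.
- ASDAS ESR = 0.630 + 1.479 = 2.11, at or above 2.1, so the flare definition is met.

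The ESR at which ASDAS ESR reaches 2.1 is ((2.1 − 0.35x) / 0.29)². With CRP at 2 mg/L:

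| Items (cm) | ASDAS CRP | ESR giving ASDAS ESR 2.1 (mm/h) |
|---|---|---|
| 1.0 | 1.00 | 36.4 |
| 1.5 | 1.18 | 29.5 |
| 1.8 | 1.29 | 25.7 |

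Over all symptom patterns at the entry limit with CRP 2, the lowest such ESR is 19.5 mm/h. That needs all the symptom burden on the peripheral item. With no symptoms it is 52.4. Without the SAP floor the requirement is lower: at CRP 0.5 with equal items at the entry limit (2.94 cm), about 13.6 mm/h.

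**How many entrants?** The documents give no ESR distribution. As a range only, a simulation was run on assumed lognormal values:
- CRP median 1.5 mg/L, geometric SD 2.5.
- ESR median 6 to 15 mm/h, geometric SD 2.0 to 2.5, correlation with CRP on the log scale 0.3 to 0.6.
- Symptoms centred on 1.5 cm.

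With and without the floor, between 0.1% and 16% of entrants had ASDAS ESR of 2.1 or more at entry. None of these inputs comes from the plan.

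**Effect on the flare proportion.** A discordant entrant adds to the count only if that subject would not otherwise have flared.
- If 70% would flare anyway: (1 − 0.70) / 96 = 0.31 point each. Three subjects add 0.9 point; ten add 3.1.
- If none would otherwise flare (upper bound): 1 / 96 = 1.04 points each.
- As a share q of entrants, the shift is 0.30q: 5% gives 71.5%, 10% gives 73.0%, 20% gives 76.0%.

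**The case against.** **Existing analyses already cover part of this.** Every subject with Week 24 ASDAS ESR of 2.1 or more falls outside the sustained group, whose members all start at least 0.8 below the cut. A reader might infer that the plan never looks at ASDAS ESR at withdrawal. That is true of eligibility and the primary analysis but not of the supportive work. The cover is partial, however. The sustained group also needs a Week 12 or 16 response, so a difference in flare rates mixes durability of response with disagreement between scores. The by-visit ASDAS ESR summaries do not count entrants at or above 2.1. Adjustment in a Cox model does not correct a single-arm proportion.

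**An ESR-based flare rule suits the workflow.** ESR is measured at the site and CRP centrally (Protocol 7.6), and retreatment can start at an unscheduled visit at which flare is found (Protocol 3.3). This is a fair reason for the rule, and nothing here argues for changing it.

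**The reference cohort meets the same entry requirements (SAP 5.2.4).** Discordance can therefore occur in both studies, but it need not cancel. With an assumed 5% discordant in each, 70% becomes 71.5%, while an assumed 10% reference rate becomes 0.05 + 0.95 × 0.10 = 14.5%.

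**Entrants just below the cut.** With items at 1.5 cm and ESR 20, ASDAS ESR is 1.82. Items at 2.3 cm bring it to 2.10 while ASDAS CRP (CRP 2) is 1.47. A reader might call this a flare without change in disease, and set the rise of 0.28 against the 1.1 in SAP 3.2. The documents do not support that reading. A rise of 0.8 cm on all four items is worsening, and 1.1 is a threshold for improvement from baseline.

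**Conclusion.** The point holds as a gap in the supportive analyses. The formulas allow a subject to enter Period 2 while meeting the flare definition, and no planned analysis of the primary proportion identifies or removes such subjects.

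The size is modest on plausible counts: about 0.9 to 3.1 points for 3 to 10 subjects, against a half-width of 9 to 10. This assumes that affected subjects would otherwise flare at the planned 70%. For time to flare, an affected subject becomes an event at about four weeks even where a true flare would have come later.

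Two stronger readings go beyond the documents. One is that some entrants will in fact be at the threshold. Without an ESR distribution the number could be close to zero, and any clustering of such flares at Week 28 is likewise unquantified. The other is that each such entrant adds a full percentage point. That is the ceiling, reached only if none of them would have flared anyway.

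**What to change.** Keep the primary definition and every clinical rule. In SAP 6.1.1.1:

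1. Tabulate Week 24 ASDAS ESR for all Period 2 entrants, with the number at 2.1 or above.
2. Repeat the flare proportion, Kaplan-Meier and Cox analyses excluding subjects with Week 24 ASDAS ESR of 2.1 or more, in both studies, and report them beside the primary result.
3. Optionally, report how many flares also had ASDAS CRP of 2.1 or more at the flare visit, as a descriptive lower bound only. Subjects who flare on ASDAS ESR alone go on to retreatment, so a later off-drug flare on ASDAS CRP cannot be observed. The text should say that they are not confirmed non-flares.

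The cost is SAP wording and a few tables. ESR, hsCRP and the items are already scheduled at Week 24 and at every Period 2 visit. The supportive analysis loses a little precision: with 10 of 96 excluded, the half-width at 70% is 1.96 × √(0.21 / 86) = 9.7 points instead of 9.2. If the table shows few or no such entrants, it supports the primary result directly.
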